17.6 CGI-Severity (CGI-S) / CGI-Improvement (CGI-I)

CGI-Severity (CGI-S)

Considering your total clinical experience with this patient population, how sleepy is the patient at this time?

- 1. Normal, not at all sleepy
- 2. Borderline sleepy
- 3. Mildly sleepy
- 4. Moderately sleepy
- 5. Markedly sleepy
- 6. Severely sleepy
- 7. Among the most extremely sleepy patients

CGI-Improvement (CGI-I)

Compared to the patient's condition at BASELINE, this patient's condition is:

- 1. Very much improved
- 2. Much improved
- 3. Minimally improved
- 4. No change from baseline
- 5. Minimally worse
- 6. Much worse
- 7. Very much worse

17.7 Epworth Sleepiness Scale

Epworth Sleepiness Scale

Name: _____ Today's date: _____

Your age (Yrs): _____ Your sex (Male = M, Female = F): _____

How likely are you to doze off or fall asleep in the following situations, in contrast to feeling just tired?

This refers to your usual way of life in recent times.

Even if you haven't done some of these things recently try to work out how they would have affected you.

Use the following scale to choose the **most appropriate number** for each situation:

- 0 = would **never** doze
- 1 = **slight chance** of dozing
- 2 = **moderate chance** of dozing
- 3 = **high chance** of dozing

It is important that you answer each question as best you can.

Situation	Chance of Dozing (0-3)
Sitting and reading _____	—
Watching TV _____	—
Sitting, inactive in a public place (e.g. a theatre or a meeting) _____	—
As a passenger in a car for an hour without a break _____	—
Lying down to rest in the afternoon when circumstances permit _____	—
Sitting and talking to someone _____	—
Sitting quietly after a lunch without alcohol _____	—
In a car, while stopped for a few minutes in the traffic _____	—

THANK YOU FOR YOUR COOPERATION

© M.W. Johns 1990-97

4.7 Safety Analyses23

████████████████████24

████████████████████25

████████████████████28

LIST OF ABBREVIATIONS AND DEFINITION OF TERMS

%	Percentage
ADR	Adverse Drug Reaction
AE	Adverse Event
CGI	Clinical Global Impression
CR	Controlled Release
█	█
eCRF	Electronic Case Report Form
EDS	Excessive Daytime Sleepiness
█	█
FAS	Full Analysis Set
FWER	Family-Wide Error Rate
FT218	Sodium oxybate for extended-release oral suspension
█	█
ICH	International Conference on Harmonization
IMP	Investigational Medicinal Product
ITT	Intent To Treat
MMRM	Mixed-effects Model for Repeated Measures
MWT	Maintenance of Wakefulness Test
NCA	Number of Cataplexy Attacks
NT1	Narcolepsy Type 1
NT2	Narcolepsy Type 2
PGI	Patient Global Impression
PPS	Per Protocol Set
PSG	Polysomnogram

PT	Preferred Term
SAE	Serious Adverse Event
SAP	Statistical Analysis Plan
SSDD	Sleep and Symptom Daily Diary
SOC	System Organ Class
■	■
SS	Safety Set
TEAE	Treatment Emergent Adverse Event
TESAE	Treatment Emergent Serious Adverse Event
TFL	Tables, Listings and Figures
VAS	Visual Analog Scale

1 INTRODUCTION

Sodium Oxybate is indicated for the treatment of excessive daytime sleepiness (EDS) and cataplexy in adults with narcolepsy. Flamel proposes a new sodium oxybate drug product based on its Micropump® technology, Sodium oxybate for extended-release oral suspension (FT218), to be taken once at bedtime. Sodium Oxybate has shown significant efficacy for treating EDS and cataplexy in narcolepsy.

1.1 STUDY RATIONALE

This study was designed as a pivotal efficacy study. The background data used to design the trial was obtained from a Phase I (PKFT218-1301) pharmacokinetic study in healthy volunteers. In that study the 4.5 g FT218 formulation was associated with a safety profile and total exposure similar to the reference marketed drug product, Xyrem®. Also, no safety concerns emerged with the FT218 formulation at 6 g and 7.5 g. The study confirmed the expected PK properties of the FT218 formulation, i.e. a drug release over 6 hours, a lower C_{max} and a residual plasma level at 8 hours after intake that was not significantly different from Xyrem®. These results indicate that the FT218 formulation should be as safe as Xyrem®. Overall, the PK profile of FT218 at 4.5 g, 6 g, and at 7.5 g supports the hypothesis that the IMP is as safe as the reference, Xyrem®.

The forced up-titration design is intended to inform an appraisal of the benefits and risks of increasing doses. Three target therapeutic dose levels will be tested since a concentration/response relationship has not been established. The 6 g, 7.5 g and 9 g doses were selected for their safety and efficacy profile in treating patients with EDS and cataplexy; the study formulation has been found to be safe at 4.5 g, 6 g and 7.5 g in healthy volunteers. The up-titration schedule from 4.5 g/night to 6 g/night is based on the dosage schedule recognized as safe with the reference product. Further 1.5 g increments commence after a period sufficiently long to permit evaluation of efficacy. Subjects remain on the 6 g dose for two weeks, on the 7.5 g dose for five weeks and on the 9 g dose for five weeks.

1.2 CHANGES FROM PROTOCOL

N.A. This is a Special Protocol Review.

1.3 DEFINITION OF ANALYSIS POPULATION

The target population is individuals in need of treatment of EDS and cataplexy in patients with narcolepsy. The full analysis population for efficacy is the intent to treat population including all randomized subjects with at least one efficacy measurement at the time of the 6 g dose (whether FT218 or placebo.)

2 STUDY SUMMARY

This is a double-blind, randomized, placebo controlled, two arm multi-center forced up-titration study to assess the efficacy and safety of a once nightly formulation of Sodium Oxybate (FT218) for the treatment of EDS and cataplexy in patients with narcolepsy. The active arm will have forced dose increments at fixed times from 4.5 g/night followed by 1.5 g/night increments until the final 9 g dose is reached. Subjects will remain on the 4.5 g dose for one week, the 6 g for two weeks, the 7.5 g for five weeks and the 9 g dose for five weeks. The primary contrasts are between the 9 g dose and the corresponding placebo outcomes. If the 9 g dose is statistically significant, the 7.5 g dose and the corresponding placebo outcomes will be compared. If the 7.5 g dose is statistically significant, the 6 g dose and the corresponding placebo outcomes will be compared.

There are two types of narcolepsy patients to be studied. Patients with Narcolepsy Type 1 (NT1) who present with excessive daytime sleepiness (EDS) and cataplexy and patients with Narcolepsy Type 2 (NT2) who present with EDS (without cataplexy). For both NT1 and NT2, the historical Multiple Sleep Latency Test (MSLT) must indicate 2 or more sleep-onset REM periods (SOREMPs), the mean sleep latency on MSLT must be in the pathological range (i.e. <8 minutes) and no other sleep disorder better explains the EDS.

The endpoints for evaluating EDS in both NT1 and NT2 narcolepsy patients are the mean sleep latency on the Maintenance of Wakefulness Test (MWT), and the Clinician Global Impression (CGI) for sleepiness. The endpoint for evaluating cataplexy in NT1 narcolepsy patients is the number of cataplexy attacks (NCA) obtained from the Sleep and Symptom Daily Diary.

2.1 OBJECTIVES

To compare the safety and efficacy of 6 g, 7.5 g and 9 g doses of FT218 to placebo in the treatment of symptoms in patients with Narcolepsy.

2.1.1 PRIMARY OBJECTIVES

- To compare the efficacy of 6.0, 7.5, and 9.0 g of FT218 to placebo in treating EDS in both NT1 and NT2 subjects as measured by mean sleep latency on the Maintenance of Wakefulness Test (MWT) and by the Clinical Global Impression (CGI) rating of sleepiness
- To compare the efficacy of 6.0, 7.5, and 9.0 g of FT218 to placebo in treating cataplexy in NT1 subjects as measured by the number of cataplexy attacks (NCA) determined from the cataplexy frequency item in the Sleep and Symptom Daily Diary

2.1.2 SECONDARY/EXPLORATORY OBJECTIVES

The secondary/exploratory objectives of the study are to compare the efficacy of 6.0, 7.5, and 9.0 g of FT218 to placebo for [REDACTED]

[REDACTED]

2.1.3 SAFETY OBJECTIVE

To evaluate the relative safety of the 6 g, 7.5g and 9 g doses of FT218 compared to placebo.

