7.3 Safety Objective

The safety objective of the study is:

- To evaluate the relative safety of FT218 compared to placebo.

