11.10 Safety Analysis

Safety evaluation will be conducted on the S population and using the same evaluation period as for efficacy analysis.

Safety will be evaluated based on reports of AEs either spontaneously reported or observed in clinical laboratory analyses. They will be coded according to the MedDRA.

Adverse events will be summarized based on number and percentages of subjects with any AEs, SAEs, and permanent withdrawal from the study. Adverse events will also be tabulated by SOC and preferred term.

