2.2 STUDY DESIGN

This is a double-blind, randomized, placebo controlled, two arm multi-center forced up-titration clinical trial to assess the efficacy and safety of a once per night formulation of Sodium Oxybate (FT218) for the treatment of EDS and cataplexy in patients with narcolepsy. The active arm will have forced dose increments at fixed times from 4.5 g/night followed by 1.5 g/night increments until the final 9 g dose is reached. Subjects in the active arm will remain on the 4.5 g dose for one week, 6 g for two weeks, 7.5 g for five weeks and the 9 g dose for 5 weeks.

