4.1.5 TABLES, LISTINGS AND FIGURE PRESENTATION

The treatment groups will be displayed in the tables, listings and figures as

Group 1:	9 g	(Period 3c (i) and 3c (ii), weeks 9-13)
Group 2:	Placebo	(Period 3c (i) and 3c (ii), weeks 9-13)
Group 3:	7.5 g	(Period 3b (i) and 3b (ii), weeks 4-8)
Group 4:	Placebo	(Period 3b (i) and 3b (ii), weeks 4-8)
Group 5:	6 g	(Period 3a, weeks 2-3)
Group 6:	Placebo	(Period 3a, weeks 2-3)

The listings will display all of the data contained in the eCRF. The listings will be ordered by the treatment groups shown above.

Summaries of continuous variables will use the following descriptive statistics: n, mean, standard deviation, 95% confidence interval of the mean, median, interquartile range, minimum and maximum.

The number of decimal places to be displayed for each statistic will be as follows:

- Mean, 95% confidence intervals, median and interquartile range: one more decimal place than data.
- Standard deviation: two more decimal places than the data.
- Minimum and maximum: same number of decimal places as the data.
- P-value: 3 decimal places, if less than 0.001 then display as “<0.001”.

Categorical variables will be presented as frequency counts and percentages. Percentages will be displayed to one decimal place throughout.

All dates will be displayed in the format DDMMYYYY

Calculations using dates will follow these conventions:

The relative study day of the event (DAY) is calculated as the difference between the date of the event of interest (EVENT DAY) and the date of first dose of study medication (FIRST DOSE), i.e.

$$\text{DAY} = \text{EVENT DATE} - \text{FIRST DOSE} + 1 \quad \text{for EVENT DATE} \geq \text{FIRST DOSE}$$

$$\text{DAY} = \text{EVENT DATE} - \text{FIRST DOSE} \quad \text{for EVENT DATE} < \text{FIRST DOSE}$$

Durations will be calculated by: $\text{DURATION} = (\text{STOP DATE} - \text{START DATE}) + 1$

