4.7 SAFETY ANALYSES

Safety evaluations will be performed on the safety population using the actual treatment administered.

Adverse events will be identified as treatment-emergent (TEAE) if the event occurs or increases in severity after the first dose of study medication is taken. Adverse events will be identified as mild, moderate or severe and related to the treatment as reported on the CRF. The adverse events will be assigned a preferred term (PT) and a system organ class (SOC) according to the Medical Dictionary for Regulatory Activities (MedDRA), latest version. In counting the number of events reported, a continuous event, i.e., an event reported more than once and which did not cease, will be counted only once with the worst recorded severity. Non-continuous AEs reported multiple times by the same subject will be counted as multiple events. AEs will be assigned to the period of the study corresponding to the time of onset. Events presenting immediately prior to the first dose of study medication that do not worsen in severity, will not be included. In deriving the tabulation relating to preferred term reporting, the severity of a recurrent AE will be taken to be the most severe and the relationship to study medication as the most probable within the relevant period of the study. Total exposure to FT218 will be determined in terms of number of days and dose.

Laboratory data will be summarized in terms of the proportions of patients with clinically notable abnormalities using normal ranges. Shift tables will tabulate baseline to most extreme post baseline values. Summary statistics of raw data and change from baseline values will be obtained including means, medians, standard deviations and ranges will be produced.

The summaries will include subjects in the safety population who have had at least one laboratory test performed after the first study drug administration with an available baseline laboratory value. Baseline values will be measured as the last available measure before taking study drug.

[REDACTED]

[REDACTED]

[REDACTED]

[REDACTED]

[REDACTED]

[REDACTED]

[REDACTED]

[REDACTED]

[REDACTED]

[REDACTED]

[REDACTED]

[REDACTED]

[REDACTED]

[REDACTED]

[REDACTED]

[REDACTED]

[REDACTED]

[REDACTED]

[REDACTED]

[REDACTED]

[REDACTED]

[REDACTED]	[REDACTED]	[REDACTED]
[REDACTED]	[REDACTED]	[REDACTED]
[REDACTED]	[REDACTED]	[REDACTED]
[REDACTED]	[REDACTED]	[REDACTED]
[REDACTED]	[REDACTED]	[REDACTED]
[REDACTED]	[REDACTED]	[REDACTED]

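### By-dose adverse event percentages cover 2 weeks at 6 g but 5 weeks at 7.5 g and 9 g, so 6 g can look safer than the higher doses from window length alone

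*SAP*

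**What the plan says.** SAP 2.1.3 gives the safety objective as "To evaluate the relative safety of the 6 g, 7.5g and 9 g doses of FT218 compared to placebo". The protocol's own objective (7.3) is at arm level: "To evaluate the relative safety of FT218 compared to placebo". SAP 1.1 gives the reason for the titration: "The forced up-titration design is intended to inform an appraisal of the benefits and risks of increasing doses".

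SAP 2.2 fixes time at dose after the first week at 4.5 g: "6 g for two weeks, 7.5 g for five weeks and the 9 g dose for 5 weeks". SAP 4.1.5 defines the groups for tables. The 6 g group and its placebo group are "Period 3a, weeks 2-3"; the 7.5 g pair is "Period 3b (i) and 3b (ii), weeks 4-8"; the 9 g pair is weeks 9-13. SAP 4.1.3 confirms that each dose is set against placebo from the matching weeks, and SAP 4.1 asks for descriptive statistics by dose group.

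On AEs, Protocol 11.10 says "Adverse events will be summarized based on number and percentages of subjects with any AEs, SAEs, and permanent withdrawal from the study", over the evaluation period used for efficacy. SAP 4.7 says "AEs will be assigned to the period of the study corresponding to the time of onset", counts repeated separate events as multiple events, and derives exposure to FT218 in days and dose. No readable sentence uses that exposure as a denominator for AEs, and none states the by-dose denominator.

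**The concern.** Read together, these sections lead to AE tables by dose group in which one dose is observed for 2 weeks and two doses for 5. The longer a window, the more subjects will have at least one event in it, whether or not risk per week has changed. A reader using the tables as SAP 1.1 intends, to weigh benefit against risk as dose rises, will compare columns and may take a step from 6 g to 7.5 g as a dose effect. Protocol 6.6 reports that several AEs of sodium oxybate are dose-related and most pronounced at the highest dose, so a gradient is expected and an artefact could easily pass as one. SAP 4.6.2 also uses 6 g to address the minimally effective dose, which makes its safety relative to the higher doses a natural question.

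**Working it through.** **Inputs from the documents.** Time at dose is 2, 5 and 5 weeks after 1 week at 4.5 g (SAP 2.2); 1 + 2 + 5 + 5 = 13 weeks, which agrees with the stated treatment period. Display windows are weeks 2-3, 4-8 and 9-13 (SAP 4.1.5), with concurrent placebo. The readable text gives no AE rate, so there is no figure of the plan's own to reproduce.

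**Assumption.** Weekly onset hazard h is not in the documents. I take 1% to 10%, constant and equal at all doses, and then relax constancy.

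**Step 1: crude percentage.** P(at least one onset in t weeks) = 1 − exp(−h·t). For h = 0.05: 1 − exp(−0.10) = 9.5% over 2 weeks and 1 − exp(−0.25) = 22.1% over 5 weeks.

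| Weekly hazard | 6 g (2 weeks) | 7.5 g or 9 g (5 weeks) | Ratio |
|---|---|---|---|
| 1% | 2.0% | 4.9% | 2.46 |
| 2% | 3.9% | 9.5% | 2.43 |
| 5% | 9.5% | 22.1% | 2.32 |
| 10% | 18.1% | 39.3% | 2.17 |

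Expected event counts per subject scale by the full 5/2 = 2.5. Between 7.5 g and 9 g the ratio is 1.00.

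**Step 2: against concurrent placebo.** Let FT218 double the placebo hazard equally at every dose.

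| Placebo hazard | 6 g v placebo | Excess (points) | 7.5 g or 9 g v placebo | Excess (points) | Ratio of excesses | Risk ratio, 2 weeks then 5 weeks |
|---|---|---|---|---|---|---|
| 1% | 3.9% v 2.0% | 1.9 | 9.5% v 4.9% | 4.6 | 2.39 | 1.98, 1.95 |
| 2% | 7.7% v 3.9% | 3.8 | 18.1% v 9.5% | 8.6 | 2.29 | 1.96, 1.90 |
| 5% | 18.1% v 9.5% | 8.6 | 39.3% v 22.1% | 17.2 | 2.00 | 1.90, 1.78 |

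(Ratios are from unrounded values.) With a hazard ratio of 1.5 in place of 2, the ratios of excesses are 2.41, 2.32 and 2.07. If FT218 adds no risk, the excess is 0 and the risk ratio 1.00 at every dose.

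**Step 3: onset clustered after each step.** Let cumulative hazard follow a Weibull form restarted at each dose, H(5) = H(2) × 2.5^k. With 10% or 20% affected in 2 weeks, k = 0.5 gives 15.3% or 29.7% at 5 weeks (ratios 1.53 and 1.49); k = 0.25 gives 12.4% or 24.5% (1.24 and 1.22). If every onset falls in the first 2 weeks of a step, the ratio is 1.0.

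**Step 4: what the remedies do.** Under constant hazard, an exposure-adjusted rate returns the same value at all doses (5 per 100 subject-weeks for h = 0.05), and so does a table of the first 2 weeks at each dose (9.5%). Under early onset with k = 0.5, the 2-week table is still equal across doses, but the rate is not. Its 2-week to 5-week ratio is [H(2)/2] ÷ [H(2) × 2.5^0.5/5] = 2.5/1.58 ≈ 1.6, so 6 g would look about 1.6 times worse. Equal windows should therefore lead, with rates in support.

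**The case against.** The objective compares each dose with placebo, not one dose with another, and the placebo columns cover the same weeks. That contrast is fair as planned. The placebo column lengthens visibly with the active one, the risk ratio hardly moves, and with no excess risk nothing false appears. The protocol's objective is not by dose at all, safety here is descriptive, and no test depends on it. All of this stands, and it limits the point to the reading of 6 g against the higher doses on the percentage-point scale. It does not remove the point, because SAP 1.1 declares an interest in risk as dose rises and the excess over placebo in points still grows with the window.

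It can also be said that no single sentence specifies a crude AE table by dose. The percentages sentence in Protocol 11.10 mentions no dose, and SAP 4.7 speaks of period. Taken literally, the named periods are 3a (weeks 1-3, including the 4.5 g week), 3b(i) (4-5), 3b(ii) (6-8), 3c(i) (9-10) and 3c(ii) (11-13), giving windows of 3, 2, 3, 2 and 3 weeks. This ambiguity is real. The dose-group reading is the more natural one, given SAP 4.1 and 4.1.5 and Protocol 11.10, but the SAP should say which applies. On the dose-group reading, week-1 AEs belong to none of the six groups.

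A reader might infer that the plan has no exposure adjustment. The documents do not support that: SAP 4.7 already counts events and derives exposure by days and dose, and text after it is redacted.

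**Conclusion.** The point holds in a limited form. On the dose-group windows, the crude 6 g percentage and its excess over placebo can fall below those at 7.5 g and 9 g through window length alone. The size is about 2.0 to 2.5 times under an assumed constant and equal weekly risk, about 1.2 to 1.5 times for the crude percentage if onsets cluster early, and nil if all fall within the first 2 weeks of each step. The hazards are assumptions; the 2, 5 and 5 weeks are not.

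A reader might go further and conclude that the plan is bound to show a false dose-response across all three doses, or that the comparisons with placebo are biased. Neither follows. The windows at 7.5 g and 9 g are equal, each dose-placebo pair has equal planned length, and the artefact depends on when events start. This is an inexpensive reporting improvement, not a flaw in any planned test.

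**What to change.** In SAP 4.7, unless the redacted text already does this:

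1. Tabulate AEs with new onset in the first 2 weeks at each dose (weeks 2-3, 4-5 and 9-10) beside placebo for the same weeks, with subjects entering that window as the denominator.
2. Add exposure-adjusted rates per 100 subject-weeks by dose with the concurrent placebo rate, noting that they assume roughly constant risk.
3. State that AE windows follow dose group rather than Period 3a, and show week-1 (4.5 g) AEs separately.
4. State that between-dose safety statements rest on items 1 and 2, not on crude percentages, and that dose remains confounded with time and with earlier withdrawal, which neither table removes.

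The cost is SAP wording and a few extra tables, built from dose-days that the SAP already derives and onset timing that it already needs. No new data or subjects are required. The 2-week windows leave out later-onset events, which stay in the full-period tables.

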2.2 STUDY DESIGN

This is a double-blind, randomized, placebo controlled, two arm multi-center forced up-titration clinical trial to assess the efficacy and safety of a once per night formulation of Sodium Oxybate (FT218) for the treatment of EDS and cataplexy in patients with narcolepsy. The active arm will have forced dose increments at fixed times from 4.5 g/night followed by 1.5 g/night increments until the final 9 g dose is reached. Subjects in the active arm will remain on the 4.5 g dose for one week, 6 g for two weeks, 7.5 g for five weeks and the 9 g dose for 5 weeks.

2.3 SCHEDULE OF EVENTS

The clinical trial design is comprised of four periods: screening, wash-out/baseline (which includes randomization), double-blind-treatment and follow-up. These are shown in Table 1. After randomization, the doses of the FT218 arm begins at 4.5 g where it remains for one week (Period 3a), then it is titrated to 6 g where it remains for two weeks (Period 3a), then to 7.5 g where it remains for five weeks (Period 3b (i) and 3b (ii)) and finally to 9 g for the final 5 weeks (Period 3c(i) and 3c(ii)).

[REDACTED]

Table 1. Schedule of Events				
Period	Week(s)	Phase of Study		Evaluations
1	Week -3 to Week 0	Week -3 Screening Visit Week -3 Day 1 Commence Sleep and Symptom Diary Week -1 D7 Overnight PSG and next day 4 Nap MWT		Full screening and enrolment evaluation Full Baseline Evaluation (D7 W-1 – PSG; D1 W0 Next day MWT)
2	Week 0***	Week 0 + Max 2 days Central Scoring Lab Results Week 0 D2 or D3 Randomization		
		FT218 Arm	Placebo Arm	
3a	Weeks 1-3	Week 1: 4.5g Week 2-3: 6.g	Placebo	Full Efficacy Assessment* Visit 4 (D7 Week 3 and D1 Week 4)
3b(i)	Weeks 4-5	7.5 g	Placebo	
3b(ii)	Weeks 6-8	7.5 g	Placebo	Partial Efficacy Assessment** done at Visit 5 (D1 Week 6) Full Efficacy Assessment* at Visit 6 (D7 Week 8 and D1 Week 9)
3c(i)	Weeks 9-10	9g	Placebo	
3c(ii)	Weeks 11-13	9 g	Placebo	Partial Efficacy Assessment** at Visit 7 (D1 Week 11) Full Efficacy Assessment* at Visit 8 (D7 Week 13 and D1 Week 14)
3c(iii)	Week 14	End of Study Visit (EOS)		
4	Week 15	Follow-up Visit		

1.* Full efficacy assessment occur on the last day of a period and extend into the following day of the next period.

2.** Partial efficacy assessment (MWT and PSG are excluded) occur following the first two weeks on the 7.5 g dose and following the first two weeks on the 9 g dose during respective periods.

3.*** Maximum of 2 day turnaround for PSG and MWT results from Central Scoring Laboratory

Table 2: Study Design

Screening and Baseline		Rand	Dose Titration			Dose Titration			Stable Dosing					EOS	FU		
					7.5g	7.5g	7.5g	7.5g	7.5g	7.5g	9.0g	9.0g	9.0g	9.0g	9.0g		
		Arm 1	4.5g	6g	6g												
		Arm 2	Placebo														
				Placebo	Placebo												
						Placebo	Placebo	Placebo	Placebo	Placebo							
											Placebo	Placebo	Placebo	Placebo	Placebo		
Visit 1	Visit 2*		Visit 3***	Visit 4*		Visit 5**	Visit 6*		Visit 7**		Visit 8*	Visit 9					
W-3 D1	W-1 D7 W0 D1	EOSc +2 D	W1 D1	W3 D7 W4 D1		W6 D1	W8 D7 W9 D1		W11 D1		W13 D7 W14 D1	W15 D1					
<-----3-week washout----->																	
W-3	W0		W1	W2	W3	W4	W5	W6	W7	W8	W9	W10	W11	W12	W13	W14	W15
Period 1	Period 2		Period 3a		Period 3b(i)	Period 3b(ii)		Period 3c(i)		Period 3c(ii)		Period 3c(iii)		Period 4			

Abbreviations: D = day, EOS = End of Study, EOSc = End of Screening, FU = Follow-up, Rand = randomization, W = week, W/O = Washout

